	Grade 3 (Levels consistent with myocardial infarction as defined by the manufacturer) in subjects with symptoms suggestive of acute coronary syndrome	Discontinue subject from U3-1402. Follow institutional guidelines for management of detectable troponin testing. Repeat levels should be obtained every 6 to 8 hours to identify a rising and/or falling pattern of values. Perform 12-lead ECG in triplicate. Perform additional troponin I testing by central laboratory at 6 and 12 hours (± 1 hour) after initial local troponin test. Cardiologist consult as necessary.
Electrocardiogram QT corrected interval prolonged	Grade 3 (Average QTcF ≥501 ms; >60 ms change from baseline)	Delay U3-1402 until resolved to ≤Grade 1 (QTcF ≤480 ms).  Determine if another medication the subject was taking may be responsible and can be adjusted or if there are any changes in serum electrolytes that can be corrected.  If QTcF prolongation is attributed to U3-1402, then reduce U3-1402 by 1 dose level.  Cardiologist consult as necessary.
	Grade 4 (Torsade de pointes; polymorphic ventricular tachycardia; signs/symptoms of serious arrhythmia)	Discontinue subject from U3-1402. Cardiologist consult as necessary

Table 5.2: Dose Delay Criteria and Dose Reduction for U3-1402 (Continued)

	Worst Toxicity NCI- CTCAE Version 5.0 Grade (unless otherwise specified)	Schedule Modification for U3-1402
Respiratory, thoracic and mediastinal disorders		
Pulmonary toxicity	See next column	If a subject develops radiographic changes potentially consistent with ILD/pneumonitis or develops an acute onset of new or worsening pulmonary or other related signs/symptoms such as dyspnea, cough or fever, rule out ILD/pneumonitis.
		If ILD/pneumonitis is suspected, delay U3-1402 dosing pending further evaluation and start corticosteroid treatment promptly unless clinically contraindicated.
		Evaluations must include CT (preferably high-resolution CT), and pulmonologist consultation (when the Investigator is not a pulmonologist). The following evaluations must also be obtained, as indicated:
		Infectious disease consultation as clinically indicated
		Blood culture and CBC (other blood tests could be considered as needed)
		Bronchoscopy and bronchoalveolar lavage if clinically indicated and feasible
		Pulmonary function tests
		• Pulse oximetry (SpO 2 )
		Arterial blood gases, as clinically indicated
		
 
Diffusing capacity of the lungs for carbon monoxide (DLCO), as clinically indicated
 

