		
 
One blood sample collection for PK analysis as soon as ILD is suspected, if feasible
 

		Other tests, as clinically indicated
		If a noninflammatory/infectious etiology is confirmed by the Investigator, treat accordingly and resumption of U3-1402 may occur after discussion between the Investigator and Sponsor.
		All events of ILD regardless of severity or seriousness will be followed until resolution including after drug discontinuation.

Table 5.2: Dose Delay Criteria and Dose Reduction for U3-1402 (Continued)

	Worst Toxicity NCI- CTCAE Version 5.0 Grade (unless otherwise specified)	Schedule Modification for U3-1402
Pulmonary toxicity	Grade 1	The administration of U3-1402 must be delayed. U3-1402 can be restarted only if the event is fully resolved to Grade 0:
		
 
If resolved in ≤28 days from day of onset, maintain dose.
 

		• If resolved in >28 days from day of onset, reduce dose 1 level.
		Toxicity Management:
		
 
Monitor and closely follow-up in 2 to 7 days for onset of clinical symptoms and pulse oximetry.
 

		
 
Consider follow-up imaging in 1 to 2 weeks (or as clinically indicated).
 

		Consider starting systemic steroids (eg, at least 0.5-mg/kg/day prednisone or equivalent) until improvement, followed by gradual taper over at least 4 weeks.
		If worsening of diagnostic observations despite initiation of corticosteroids, then follow Grade 2 guidelines (if subject is asymptomatic, then subject must still be considered as Grade 1 even if steroid treatment is given).
	Grade 2	Permanently discontinue subject from study treatment. Toxicity Management:
		Promptly start systemic steroids (eg, at least 1-mg/kg/day prednisone or equivalent) for a minimum of 14 days or until complete resolution of clinical symptoms and chest CT findings, followed by gradual taper over at least 4 weeks.
		Monitor symptoms closely.
		Reimage as clinically indicated.
		
 
If worsening or no improvement in clinical or diagnostic observations in 5 days,
 

		
 
Consider increasing dose of steroids (eg, 2-mg/kg/day prednisone or equivalent) and administration may be switched to intravenous (eg, methylprednisolone).
 

		
 
Reconsider additional work-up for alternative etiologies as described previously.
 

		Escalate care as clinically indicated.

Table 5.2: Dose Delay Criteria and Dose Reduction for U3-1402 (Continued)

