## 8.3.2. Pulmonary Toxicity (Interstitial Lung Disease/Pneumonitis)

If a subject develops an acute onset of new or worsening pulmonary or other related signs/symptoms such as dyspnea, cough or fever, rule out ILD/pneumonitis. If ILD/pneumonitis is suspected, delay U3-1402 dosing pending further evaluation. Refer to Table 5.2 for guidance on further evaluation and management of ILD/pneumonitis.

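### Table 5.2 leaves open whether study drug is stopped permanently when asymptomatic ILD worsens on corticosteroids, and its steroid wording for suspected and for Grade 1 ILD does not agree

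*Combined protocol and SAP*

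**What the plan says.** Section 5.4 names Table 5.2 as the source of the criteria for interrupting, restarting, reducing and stopping study drug. Its pulmonary-toxicity entry has a general row followed by rows by grade.

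- **General row, trigger:** "If a subject develops radiographic changes potentially consistent with ILD/pneumonitis or develops an acute onset" of pulmonary signs or symptoms, the site must rule out ILD/pneumonitis.
- **General row, action on suspicion:** "If ILD/pneumonitis is suspected, delay U3-1402 dosing pending further evaluation and start corticosteroid treatment promptly unless clinically contraindicated".
- **Grade 1 row, study drug:** dosing is delayed, and "U3-1402 can be restarted only if the event is fully resolved to Grade 0".
- **Grade 1 row, under its Toxicity Management subheading:** "Consider starting systemic steroids (eg, at least 0.5-mg/kg/day prednisone or equivalent) until improvement", followed by a taper. If diagnostic findings worsen although corticosteroids have been started, "then follow Grade 2 guidelines (if subject is asymptomatic, then subject must still be considered as Grade 1 even if steroid treatment is given".
- **Row for Grade 2, first line, ahead of its own Toxicity Management subheading:** "Permanently discontinue subject from study treatment".

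Section 8.3.2 gives a shorter account. Its trigger is a subject who "develops an acute onset of new or worsening pulmonary or other related signs/symptoms such as dyspnea, cough or fever, rule out ILD/pneumonitis". It then says to delay dosing on suspicion and refers to Table 5.2 for evaluation and management.

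**The concern.** For an asymptomatic subject whose findings worsen on steroids, a single sentence points to the Grade 2 row and also keeps the subject in Grade 1. Those rows have different end states for study drug: stopped for good, or possibly restarted. Two sites applying the sentence in good faith could stop one subject and re-expose a comparable one.

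ILD/pneumonitis is listed as an identified risk in Section 1.4 and is an adverse event of special interest with independent adjudication (Section 8.3.2.1), so the first stake is subject safety. The second is interpretation. Section 11.4.5.1 lists adverse events leading to permanent discontinuation. If the drug action depends on how a site reads one sentence, ILD discontinuations, and any recurrence after restart, partly reflect that reading and not only the drug.

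The steroid wording raises a similar but milder question at an earlier stage: whether treatment is expected or optional for a case found on imaging and graded 1.

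**Working it through.** No arithmetic decides this point. The check sets the rows side by side.

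**Step 1: drug action when asymptomatic ILD worsens on steroids.** Two readings fit the text.

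| | Reading A | Reading B |
|---|---|---|
| What the Grade 2 reference covers | The whole Grade 2 row; the reference is unqualified | Only Grade 2 toxicity management |
| Support | No exclusion of the drug action is stated | The instruction sits under the Grade 1 row's Toxicity Management subheading, and the Grade 2 row puts its drug action outside its own such subheading |
| Role of the parenthetical | Fixes the recorded grade only | Fixes the row that governs dosing, since Table 5.2 is organised by worst CTCAE grade |
| End state | Permanent discontinuation | Restart possible after resolution to Grade 0: same dose if resolved within 28 days of onset, one level lower if later |

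Both readings hold dosing at first. They differ on whether study drug can ever be given again.

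**Step 2: does other text decide between them?**

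- Section 5.4 sends the reader to Table 5.2, and so does Section 8.3.2. Neither adds a rule.
- Sections 5.4.1 and 5.8 bring in discussion with the sponsor when a delay would exceed 4 weeks. That may settle single cases, but it does not say what the Grade 1 row means.
- Section 5.8 also allows a stop for a significant adverse event as judged by the investigator, which again leaves the matter to judgement.

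**Step 3: steroids.** The general row applies on suspicion, and imaging changes alone can raise that suspicion. It says to "start corticosteroid treatment promptly unless clinically contraindicated", with contraindication as the only exception. The Grade 1 row, for a case already graded, only asks the site to consider steroids. No text says that the first instruction lapses on grading, or whether steroids already started continue once the case is graded 1.

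**Step 4: trigger.** Table 5.2 lists radiographic changes or symptoms. Section 8.3.2 lists symptoms only, then points to Table 5.2.

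**Step 5: size.** Section 1.2.3 reports 1 discontinuation for Grade 2 pneumonitis among 56 treated subjects at the August 2018 cut-off (1/56 = 1.8%). That is a Grade 2 event, for which the current table is clear. It does not estimate how often asymptomatic ILD worsens on steroids. The documents give no count of Grade 1 ILD, so the number affected cannot be derived.

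**The case against.** The strongest reply is that the table's layout already answers the main question. Each graded row gives the drug action first and toxicity management second. The worsening instruction is in the second part, so it borrows Grade 2 steroids and monitoring while the event stays Grade 1 for dosing. This is a natural reading, and it shows that the text is not a flat contradiction. It does not settle the matter, because the reference to the Grade 2 guidelines is unqualified and a site that takes it to mean the whole row is also reading the words as written.

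On steroids, the reply is that the two instructions belong to different stages, suspicion and confirmed grade, and differ in force only. That is fair: prompt treatment and considered treatment are not opposites. What remains is that the protocol never states the staging.

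On the trigger, the reply largely succeeds. A reader might infer that the protocol would miss asymptomatic radiographic ILD. The documents do not support this. Table 5.2 has the radiographic trigger and Section 8.3.2 refers to it. Chest CT or MRI is mandatory every 6 weeks for 24 weeks and every 12 weeks after that (Section 6.4.2). Potential ILD cases, serious or not, are reportable within 24 hours (Section 8.5) and go to adjudication. Only a wording mismatch is left.

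The practical scope is also limited, because restart already requires full resolution and long delays involve the sponsor. This narrows the room for divergence without removing it.

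**Conclusion.** The point holds as a material ambiguity of narrow scope. Table 5.2 does not say whether asymptomatic ILD that worsens on corticosteroids requires permanent discontinuation, and the two available readings end differently for the subject. The steroid instructions for suspected and for Grade 1 ILD also differ in force, with no text linking them; this reaches any suspected case that is graded 1. The trigger in Section 8.3.2 is a secondary alignment item.

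A reader might infer that Grade 1 ILD in general carries conflicting stop and restart rules. It does not: outside worsening on steroids, the Grade 1 row is clear. A reader might also use the 1.8% discontinuation figure to size the problem. It cannot serve, for the reason given above.

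The conclusion rests on the protocol text alone. The link between being asymptomatic and Grade 1 is taken from the table's own parenthetical, not from an outside grading source. Divergence between sites is a possibility that the wording allows; the documents do not show that it has occurred.

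**What to change.** The sponsor should reconcile the passages:

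1. In the Grade 1 row, state whether the reference to the Grade 2 guidelines includes the study-drug action or only the toxicity management, and whether the parenthetical governs grading alone or dosing as well.
2. Make the steroid wording in the general row and the Grade 1 row agree, or state explicitly how one follows from the other, including what happens to steroids already started when a case is graded 1.
3. As a secondary change, give Section 8.3.2 the same trigger as Table 5.2.

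This review takes no position on which clinical rule is right. The cost is a few sentences in Table 5.2 and Section 8.3.2 and a clarification letter to sites. The design, sample size and planned analyses are unaffected.

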### 3.1.7. Dose-limiting Toxicities

A DLT is defined as any TEAE not attributable to disease or disease-related processes that occurs during the DLT evaluation period (Day 1 to Day 21 in Cycle 1 of Dose Escalation Part) and is Grade 3 or above according to National Cancer Institute Common Terminology Criteria for Adverse Events (NCI-CTCAE) version 5.0, with the exceptions as defined below:

For hematological toxicities, a DLT is defined as follows:

- Grade 4 neutrophil count decreased lasting >7 days, neutrophil count decreased that requires standard therapies, such as colony stimulating factor (CSF)
- Grade ≥3 febrile neutropenia
- Grade 4 anemia
- Grade 4 platelet count decreased

- Grade  $\geq$ 3 platelet count decreased lasting >7 days
- Grade ≥3 platelet count decreased with clinically significant hemorrhage
- Grade 4 lymphocyte count decreased lasting ≥14 days

For hepatic organ toxicities, a DLT is defined as follows:

- Serum aspartate aminotransferase (AST) or serum alanine aminotransferase (ALT) >20  $\times$  upper limit of normal (ULN)
- AST or ALT >5 × ULN, if accompanied by blood bilirubin >1.5 × ULN
- In subjects without liver metastases, AST or ALT  $>5 \times$  ULN lasting >3 days
- In subjects with liver metastases, AST or ALT >5 × ULN lasting >3 days, if the baseline level was <3 × ULN
- In subjects with liver metastases, AST or ALT  $> 8 \times ULN$  lasting > 3 days, if the baseline level was  $> 3 \times ULN$

For non-hematological, non-hepatic major organ toxicities, a DLT is defined as follows:

- Symptomatic congestive heart failure (CHF)
- Left ventricular ejection fraction (LVEF) decline to <40% or >20% drop from baseline
- Other Grade ≥3 non-hematological, non-hepatic major organ toxicities

The following TEAEs are NOT considered DLTs:

- Grade 3 fatigue lasting <7 days
- Grade 3 nausea, vomiting, diarrhea, or anorexia that has resolved to Grade ≤2 within 3 days
- Isolated laboratory findings not associated with signs or symptoms including Grade 3/4 serum alkaline phosphatase (ALP) increased, hyperuricemia, serum amylase increased, and lipase increased, and Grade 3 hyponatremia lasting <72 hours developed from Grade 1 at baseline
- Grade 3 lymphocyte count decreased

If any of the above toxicities is observed during the DLT evaluation period, whether the toxicity is regarded as DLT will be determined based on consultation between the Investigator and Sponsor.

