	Worst Toxicity NCI- CTCAE Version 5.0 Grade (unless otherwise specified)	Schedule Modification for U3-1402		
Pulmonary toxicity	Grade 3 or 4	Permanently discontinue subject from study treatment.		
1 dimonary toxicity	Grade 5 of 1	Toxicity Management:		
		Hospitalization is required.		
		Promptly initiate empiric high-dose methylprednisolone IV treatment (eg, 500-1000 mg/day for 3 days), followed by at least 1.0 mg/kg/day of prednisone (or equivalent) for a minimum of 14 days or until complete resolution of clinical symptoms and chest CT findings, followed by gradual taper over at least 4 weeks.		
		Reimage as clinically indicated.		
		If still no improvement within 3 to 5 days,		
		
 
Reconsider additional work-up for alternative etiologies as described above.
 
		
		
 
Consider other immuno-suppressants and/or treat per local practice.
 
		
Endocrine disorders				
Endocrine	Grade 3	Delay dose until resolved to ≤Grade 2, then:		
disorders		If resolved in ≤14 days, resume U3-1402.		
		If resolved in >14 days, U3-1402 may be resumed after discussion and agreement between the Investigator and Sponsor.		
	Grade 4	Discontinue subject from U3-1402.		
Eye disorders				
Ocular	Grade 3	Delay dose until resolved to ≤Grade 2, then: If resolved in ≤7 days, resume U3-1402.		
		If resolved in >7 days, then reduce U3-1402 by 1 dose level.		
		Ophthalmologist consultation as clinically indicated.		
	Grade 4	Discontinue subject from U3-1402. Ophthalmologist consult as necessary.		
Renal and urinary d	isorders			
Creatinine increased	Grade 3 (>3.0 × baseline; >3.0 - 6.0 × ULN)	Delay dose until resolved to ≤Grade 1 or baseline, then reduce U3-1402 by 1 dose level.		
	Grade 4 (>6.0 × ULN)	Discontinue subject from U3-1402.		

Table 5.2: Dose Delay Criteria and Dose Reduction for U3-1402 (Continued)

	Worst Toxicity NCI- CTCAE Version 5.0 Grade (unless otherwise specified)  Schedule Modification for U3-1402		
Hepatobiliary disord	lers		
AST or ALT increased without TBL increased	Grade 2 (>3.0 - 5.0 × ULN if baseline was normal; >3.0 - 5.0 × baseline if baseline was abnormal)	Continue U3-1402. In subjects without liver metastasis, monitor AST/ALT 24 to 72 hours later, and continue regular monitoring until resolution.	
	if baseline was normal; >5.0 - 20.0 × baseline if	Delay U3-1402 dose until resolved to ≤Grade 1, then: If resolved in ≤7 days, resume U3-1402. If resolved in >7 days, then reduce U3-1402 by 1 dose level.	

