	>8.0-20.0 × ULN if baseline was normal; >8.0-20.0 × baseline level if baseline level was abnormal In subjects with liver metastases, if the baseline level was > 3 × ULN.	Delay U3-1402 dose until resolved to ≤baseline level, then:  If resolved in ≤7 days, resume U3-1402;  If resolved in >7 days, then reduce U3-1402 by 1 dose level.	
	Grade 4 (>20.0 × ULN if baseline was normal; >20.0 × baseline if baseline was abnormal)	Discontinue subject from U3-1402. Gastroenterologist or hepatologist consult as necessary.	
TBL increased	Grade 2 (>1.5 - 3.0 × ULN if baseline was normal; >1.5 - 3.0 × baseline if baseline was abnormal)	If no documented Gilbert's syndrome or liver metastases at baseline, delay U3-1402 until resolved to ≤Grade 1, then:  If resolved in ≤7 days, resume U3-1402;  If resolved in >7 days, reduce U3-1402 by 1 dose level.  If documented Gilbert's syndrome or liver metastases at baseline, continue U3-1402.	

Table 5.2: Dose Delay Criteria and Dose Reduction for U3-1402 (Continued)

	Worst Toxicity NCI- CTCAE Version 5.0 Grade (unless otherwise specified)	Schedule Modification for U3-1402
TBL increased	Grade 3 (>3.0-10.0 × ULN if baseline level was normal; >3.0-10.0 × baseline level if baseline level was abnormal)	
 
If no documented Gilbert's syndrome or liver metastases at baseline, delay U3-1402 dose until resolved to ≤Grade 1, then:
 
If resolved in ≤7 days, reduce U3-1402 by 1 dose level;
 
If resolved in >7 days, discontinue subject from U3-1402.
 

		If documented Gilbert's syndrome or liver metastases at baseline, delay U3-1402 dose until resolved to ≤Grade 2, then:  • If resolved in ≤7 days, reduce U3-1402 by 1 dose level;
		If resolved in >7 days, discontinue subject from U3-1402.
	Grade 4 (>10.0 × ULN if baseline was normal; >10.0 × baseline if baseline was abnormal)	Discontinue subject from U3-1402.
AST or ALT increased and TBL increased	AST or ALT ≥3 × ULN with simultaneous TBL >2 × ULN	Delay U3-1402 until drug-induced liver injury can be ruled out. The Investigator should consult with a gastroenterologist or hepatologist as needed, and the subject should be treated accordingly.  Monitor AST/ALT and TBL twice weekly until resolution or return to baseline.

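### Table 5.2's AST/ALT delay row for liver metastases with baseline above 3 × ULN does not work as written: for a single enzyme one limb can never apply and the other starts only above 24 × ULN

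*Combined protocol and SAP*

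**What the plan says.** Table 5.2 in Section 5.4.2 sets dose delays and reductions for AST or ALT increases without a bilirubin increase. Its legible entries use multiples of ULN when baseline was normal and multiples of baseline when it was abnormal:

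- Continue: "Grade 2 (>3.0 - 5.0 × ULN if baseline was normal; >3.0 - 5.0 × baseline if baseline was abnormal".
- Delay until Grade 1 or lower: a row of which only "if baseline was normal; >5.0 - 20.0 × baseline if" can be read on the abnormal-baseline side.
- Delay until baseline level or lower: ">8.0-20.0 × ULN if baseline was normal; >8.0-20.0 × baseline level if baseline level was abnormal In subjects with liver metastases", with the full restriction "In subjects with liver metastases, if the baseline level was > 3 × ULN". Dosing resumes if recovery takes 7 days or less; otherwise the dose drops one level.
- Discontinue: "Grade 4 (>20.0 × ULN if baseline was normal; >20.0 × baseline if baseline was abnormal".

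Section 3.1.7 gives hepatic dose-limiting toxicities in multiples of ULN. One applies to anyone: "Serum aspartate aminotransferase (AST) or serum alanine aminotransferase (ALT) >20" × ULN. For liver metastases there are two further criteria, both with the qualifier "lasting >3 days, if the baseline level was" and then a cut at 3 × ULN: more than 5 × ULN if baseline was below the cut, and more than 8 × ULN if above. These count only in the window "Day 1 to Day 21 in Cycle 1 of Dose Escalation Part", and DLT status is settled between Investigator and Sponsor. Section 3.1.9 sends adverse event management to Section 5.4, which limits dose modification to events judged related to U3-1402.

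Sections 4.1.1 and 4.1.3 admit AST/ALT up to 5 × ULN with liver metastases, so the subgroup can enter every part.

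**The concern.** The restriction on the row and its first limb exclude each other for a single enzyme. The limb that remains multiplies an already high baseline by 8, so it acts far above the level that Section 3.1.7 treats as dose-limiting for the same patients. The shared figure of 8, the shared subgroup and the shared cut at 3 × ULN point to a row written for the ULN scale that was then given the table's usual normal/abnormal wording.

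Table 5.2 governs dosing in all parts and cycles, and the number of cycles is unlimited. A site that follows it literally could keep dosing such a subject at enzyme levels that the sponsor elsewhere lists as dose-limiting. Liver enzyme rises are common with this drug: Section 1.2.3 reports AST increased in 41.1% and ALT increased in 39.3% of 56 treated subjects. Potential Hy's Law hepatotoxicity is an adverse event of special interest (Section 8.3.3).

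**Working it through.** The plan states no derived figure to reproduce; the check converts each rule to the ULN scale.

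**Inputs.** b is the single-enzyme baseline in × ULN. The row requires b > 3. The entry cap is 5. That cap is not a strict ceiling: eligibility laboratories are taken within 7 days before enrollment, while Section 11.1 defines baseline as the last value before the first dose. I therefore add b = 6 as an assumed illustration.

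**Limb 1.** It needs a normal baseline (b ≤ 1) together with b > 3. No value of b satisfies both.

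**Limb 2 and neighbouring rows.** Grade 2 runs from 3b to 5b, Grade 3 starts at 5b if it covers this subgroup, the special row starts at 8b, and Grade 4 starts at 20b.

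| b (× ULN) | Grade 2, continue | Grade 3 start, if applicable | Special row start | Grade 4 start | 8 × ULN as a fold of baseline (8/b) |
|---|---|---|---|---|---|
| just above 3 | >9 to 15 | >15 | >24 | >60 | 2.67 |
| 4 | >12 to 20 | >20 | >32 | >80 | 2.00 |
| 5 | >15 to 25 | >25 | >40 | >100 | 1.60 |
| 6 (assumed) | >18 to 30 | >30 | >48 | >120 | 1.33 |

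**Against Section 3.1.7.** The special row starts at 24/8 = 3 to 40/8 = 5 times the subgroup's 8 × ULN level, and above the 20 × ULN level that applies to anyone. The Grade 2 instruction to continue lies wholly above 8 × ULN. For b > 4 it also reaches past 20 × ULN, since 5b > 20.

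**The two readings of the Grade 3 row.**

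- If it covers this subgroup, delay begins at 5b: above 15, 20 and 25 × ULN for b = 3, 4 and 5. The special row then begins later than the general one, is redundant as a trigger, and gives a different recovery target.
- If it does not, no row for isolated AST/ALT rises acts between 5b and 8b: 15 to 24, 20 to 32 and 25 to 40 × ULN.

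The row fails to do useful work under either reading.

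**Recovery target.** The special row requires return to baseline level, whereas the Grade 3 row requires Grade 1. On the ULN scale this makes sense: Grade 1 would end at 3 × ULN, below these subjects' own baseline. On the baseline scale Grade 1 reaches 3 × baseline, so no special target is needed. This is inference, but it points the same way as Section 3.1.7.

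**Effect of moving the start to 8 × ULN.** For b = 3, 4 and 5 the delay threshold falls by 8b − 8 = 16, 24 and 32 × ULN against the row as written, or by 5b − 8 = 7, 12 and 17 × ULN if the Grade 3 row already applies.

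**The case against.** Multiples of baseline are the table's own convention for abnormal values, in the bilirubin rows as well, so using them is not in itself a mistake. An empty limb triggers no wrong dose. It is empty only for one enzyme: with AST above 3 × ULN and ALT normal, it could be read as applying to ALT. Section 3.1.7 is an endpoint definition for one cycle of one part, requires more than 3 days' duration and is subject to consultation. Choosing 8 × ULN for dose delay is a clinical judgement.

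The reach is also narrow. It needs liver metastases, a baseline above 3 × ULN, no qualifying bilirubin rise and a drug-related event. Investigator discretion (Sections 5.4 and 5.8), the combined AST/ALT-and-bilirubin row and the hepatitis B/C row give partial cover. The study is late: Version 9.0 mainly extends its duration, to the end of 2023.

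Most of this stands and limits the point. A reader might infer three stronger things that the documents do not support:

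- That Sections 3.1.7 and 5.4 give contradictory orders. They serve different purposes and need not match; 24 against 8 is not like for like, because the DLT carries the duration condition.
- That no delay occurs before 24 × ULN, or that this is the only AST/ALT row for the subgroup. Neither can be established while the Grade 3 label is unreadable.
- That the Grade 4 limit is wrong. It follows the table's convention, and nothing in the documents shows an error.

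What the objection does not do is make the row coherent. Discretion is a backstop and does not repair a row that is either redundant or leaves a gap.

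**Conclusion.** The row should be corrected. For a single enzyme its normal-baseline limb can never apply and its other limb starts only above 24 × ULN, about 40 × ULN at the entry cap. The comparison with Section 3.1.7 is evidence of the intended scale and does not create a rule that Table 5.2 must obey. The live effect is on drug-related, isolated AST/ALT rises, mainly after Cycle 1 and in the Dose Finding and Dose Expansion Parts.

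This rests on reading the row enzyme by enzyme, on baseline as defined in Section 11.1, and on entry values near the cap being possible. The documents do not give the number of subjects with baseline above 3 × ULN, so the number of doses affected cannot be estimated. My confidence is medium, because the Grade 3 label decides whether the practical gap starts from 15 to 25 × ULN or from 24 to 40 × ULN.

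**What to change.** Delete the normal and abnormal limbs. Restate the row as more than 8.0 × ULN, up to the Grade 4 limit, in subjects with liver metastases and a baseline above 3 × ULN. Keep its actions. Add one sentence giving it precedence over the baseline-multiple Grade 2 and Grade 3 entries for this subgroup. The sponsor may carry over the more-than-3-days condition from Section 3.1.7, and should decide separately whether the Grade 4 limit is as intended.

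This is one row and one sentence in one amendment. Without the duration condition it needs no new visits or tests, since safety laboratories are already drawn within 3 days before each infusion. With it, a repeat sample would be needed.

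There are two downsides:

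- A few dose delays would come earlier, after a 2.7-, 2.0- or 1.6-fold rise at baselines of 3, 4 and 5 × ULN, some of them below Grade 2 on the table's scale. Because recovery is to baseline level, a delay beyond 4 weeks may lead to withdrawal (Section 5.4.1).
- An inversion is possible. If the Grade 3 row governs abnormal baselines at or below 3 × ULN, delay there starts at 5b, which exceeds 8 × ULN once b > 1.6 and reaches 15 × ULN at b = 3. A subject at 2.5 would be delayed only above 12.5 × ULN, but one at 3.5 above 8 × ULN (8/3.5 = 2.29-fold). Aligning those rows with Section 3.1.7's 5 × ULN would remove it, at the price of rewording more of the table.
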